6.2. Demographics and Baseline Characteristics

Demographic and baseline disease characteristics will be summarized by treatment arm and overall for mITT and Safety Analysis Sets (if different).

Descriptive statistics of demographic characteristics including but not limited to: age (years), age category (<65 years vs. \geq 65 years), sex, race, ethnicity, height, weight, and body mass index (BMI) and country.

Baseline disease characteristics including but not limited to: the 24-hour UP, the 24-hour UP category (($\geq 1g/24$ -hour and < 2g/24-hour vs. $\geq 2g/24$ -hour), UPCR as measured in 24-hour urine and in spot urine, eGFR (mL/min/1.73m²), eGFR category (30-44, 45-59, 60-89, \geq 90) (mL/min/1.73m²), eGFR category (30-59, \geq 60) (mL/min/1.73m²), blood pressure (SBP and DBP), age at diagnosis, time from diagnosis to randomization, MEST-C score, IgA, IgG, IgM, C3, C1q, C4d, and C5b-9.

6.3. Medical History, Prior and Concomitant Medications

Medical history, prior and concomitant medications will be summarized for the Safety Analysis Set.

The medical history data will be coded with the Medical Dictionary for Regulatory Activities (MedDRA version 21.1 or higher). The number and percent of subjects by System Organ Class (SOC), high level term (HLT) and Preferred Term (PT) will be summarized by treatment group and overall. Prior and concomitant medications will be coded with the World Health Organization (WHO) Drug Dictionary (September 2018 or later).

Prior medications are defined as medications that were taken prior to the first dose of study drug (cemdisiran or placebo). Concomitant medications are defined as medications which were taken prior to and were ongoing while on study drug or medication(s) taken on or after the first dose date of the study drug.

Tabular summary of the number and percentage of subjects taking concomitant medications will be summarized by anatomic therapeutic class (ATC) and preferred term. Listing will be provided for medical history, prior and concomitant medications.

6.4. Drug Exposure

The following variables are summarized using Safety Analysis Set but not limited to; the total number of doses received and missed per patient, mean number of dosing per patient, duration of drug exposure (weeks), and cumulative drug exposure time (person years).

Drug exposure (days) will be defined as [Exposure time= (date of last exposure – date of first dose +1)] where date of last exposure will represent either the date of the last administered dose +28, analysis cut-off date or end of study date, whichever is earliest. The exposure during the DB period will be right censored; that is, the date of the last exposure will not be later than the first date of dosing in the OLE period. Dose interruptions and compliance are not taken into account.

Drug exposure for the all cemdisiran treated set will be summarized in a similar way as in the DB period.

7. STATISTICAL ANALYSIS

7.1. Primary Endpoint

The primary endpoint of the study is the percent change from baseline in urine protein/creatinine ratio [UPCR] as measured in 24-hour urine at Week 32. The analysis will be conducted using the modified ITT analysis set.

Valid 24-hour urine protein values collected during the DB period will be included in the primary analysis (1 valid assessment at week 16 visit and the mean of two valid assessments at baseline and week 32 visit). All 24-hour urine samples need to meet the validity criteria below (Section 6.4.1.1 of the protocol). The 24-hour UPCR at baseline or Week 32 is the average of two valid collections.

A 24-hour urine collection will be considered valid if the following criteria are met:

- The collection is between 22-26 hours in duration between the initial discarded void and the last void or attempt to void.
- No voids are missed between the start and end time of the collection as indicated by the patient's urine collection diary.

The resulting 24-hour UPCR at each visit will be log transformed for analyses.[Fellstrom 2017; Li 2006] The primary analysis will be performed using a restricted maximum likelihood (REML) based Mixed-Effect Model Repeated Measures (MMRM) approach. The outcome variable is change from baseline in 24-hour UPCR in log-scale at week 16 and week 32 visits. Analysis will include fixed effects of treatment (cemdisiran vs. placebo), scheduled visits (week 16 and week 32), interaction term of treatment and scheduled visits, baseline 24-hour UPCR in log-scale (continuous), and patient as a random effect. Unstructured working correlation will be used to model the within-patient errors. If the fit of covariance structure fails to converge, independent correlation structure will be used. At each visit, least square (LS) means ($\hat{\mu}_j$) with corresponding standard errors (SEM) and 90% CI will be displayed by treatment arm. The primary comparison is the LS mean treatment difference (cemdisiran – placebo) in percent change of 24-hour UPCR at week 32 visit from baseline. This LS mean difference will be presented along with corresponding standard errors (SEMs), 90% CIs and p-value from the model.

The following results will also be presented:

• Placebo-adjusted geometric mean percent change at week 32 visit:

$$\frac{GM \left(\frac{UPCR \text{ at week32}}{UPCR \text{ at baseline}}\right)_{cemdisiran} - GM \left(\frac{UPCR \text{ at week32}}{UPCR \text{ at baseline}}\right)_{placebo} * 100}{GM \left(\frac{UPCR \text{ at week32}}{UPCR \text{ at baseline}}\right)_{placebo}} * 100$$

= $[\exp(\delta) - 1] * 100$, where δ is the LS mean treatment difference between the two arms from the MMRM model in log-scale above.

• The 90% CI for the placebo-adjusted geometric mean percent change:

[(exp(lower bound for δ) - 1) * 100, (exp(upper bound for δ) - 1) * 100]

In addition, the geometric mean for the ratio to baseline at week 32 visit in 24-hour UPCR and 90% confidence intervals for each treatment group will be presented using respective LS means $(\hat{\mu}_i)$ and corresponding 90% confidence intervals (j=0 if placebo and j=1 if cemdisiran):

 $exp(\hat{\mu}_{j})$ and $\left[exp(lower bound for \mu_{j}), exp(upper bound for \mu_{j})\right]$

Descriptive statistics will also be generated for 24-hour UPCR (in original scale and log scale) by treatment arm at each scheduled visit during DB and OLE and plotted. Model adjusted geometric mean (with 90% CI) figures of the ratio to baseline by treatment arm will be plotted as well as individual spaghetti plots.

The 24-hour UPCR data will also be summarized descriptively to evaluate the long-term efficacy of cemdisiran using the All Cemdisiran Treated Analysis Set.

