2. STUDY OVERVIEW

2.1. Study Design

This study is a multicenter, double-blind, placebo-controlled study comprised of three periods (Figure 1). Eligible patients will begin a 14-week observational run-in period during which treatment with the standard of care is expected to remain unchanged. At the end of run-in period, patients whose average urine protein (UP) of two valid urine collections is at or higher than 1g/24-h are eligible for randomization into the 36-week double blind (DB) period. Approximately 30 patients are planned to be randomized in a 2:1 ratio, 20 in the cemdisiran arm and 10 in the placebo arm in the DB period, which is followed by a 156-week open-label extension (OLE) period to further evaluate the long-term safety and efficacy. All patients will be followed for safety for 52 weeks after the end of study visit.

The independent Data Monitoring Committee (DMC) will have access to subject level treatment assignments and perform periodic reviews of unblinded data throughout. Details are provided in the DMC Charter of the study.

Figure 1 Study Design

days)	Run-in Period (14 Weeks)		Treatment 1 (36 Wee	Freatment Period (36 Weeks)		sment	Open-label Extension (156 Weeks)		iod	
Screening (up to 120 c	Standard of care	mization (2:1	ALN-CC5 600mg Q4W (n=20) + Standard of care)T k 32)	S ¢ 36)	ndpoint asses	ALN-CC5	DT (c 184) 0S (s 188)	SS (188)	ty Follow-up (2 Weeks)
		Rando	Placebo (n=10) + Standard of care	EC (Wee	EC (Wee	Primary e	+ Standard of care	EC (Week	EC (Week	Safe (5

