5. GENERAL STATISTICAL METHODS

5.1. Sample Size Justification

The sample size of the study was determined based on the precision of the estimate of the treatment effect for the primary endpoint – the percent change from baseline in urine protein/creatinine ratio [UPCR(mg/mg)] as measured in 24-hour urine at Week 32. It should be noted that geometric mean ratio of UPCR at Week 32 to baseline is statistically equivalent to mean of the change from baseline in logarithm of UPCR. Therefore, the effect size of the study is defined as the difference of change from baseline between cemdisiran and placebo in the logarithm of UPCR.

Based on the NEFIGAN study, [Fellstrom 2017] we assume that in the placebo arm the geometric mean ratio of UPCR at Week 32 to baseline is 0.88 (log standard deviation [SD] 0.597), corresponding to a 12% reduction, while the geometric mean ratio is 0.5, or a 50% reduction for the cemdisiran arm. Using these assumptions, sample size of 9 and 18 in the placebo and cemdisiran arms will provide a width of 0.80 (+/- 0.4) for the 90% confidence interval (CI) for treatment effect size estimate (cemdisiran – placebo) in log scale.

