5.4. Randomization Stratification Factors

The randomization will be stratified based on the baseline 24-hour UP ($\geq 1g/24$ -hour and <2g/24-hour versus $\geq 2g/24$ -hour). The mean of two valid 24-hour urine protein assessments at week -2 visit will be used to determine the stratification. The stratification factor will be recorded in both the IRS and the clinical database.

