8. CHANGES TO PLANNED ANALYSES

Key changes to analyses described in the protocol are listed in the table below.

Change from Protocol	Detailed Description/Rationale
The primary analysis	To allow use of all the data when
 The analysis method is changed to MMRM 	modeling the primary endpoint, including
model, instead of linear model based on	patients who may not have Week 32
Week 32.	data. Additionally, since the baseline 24-
 Use only the continuous baseline value of 	hour urine protein and the stratification
24-hour urine protein as a covariate in the	factor are correlated, the primary analysis
model (removing the randomization	model, MMRM only includes the
stratification factor 24-hour urine protein <2	continuous baseline 24-hour urine
g/24-hours vs. ≥ 2 g/24-hours).	protein.

Change from Protocol	Detailed Description/Rationale
 Change to the sensitivity analysis Remove per-protocol analysis (Protocol Section 7.2.1) Add an additional analysis (Protocol section 7.2.5.1) 	 Per protocol analysis set is not defined for this study New sensitivity analysis is added to evaluate the sensitivity of the treatment effect by the normality assumption of the log-transformed UP data and missing data
 Change to "treatment arm" from "dose level" Correct the error in "The extent of exposure will be summarized by dose level and overall" (Protocol Section 7.2.8) 	There is only 1 dose level and it is corrected to treatment arm

9. **REFERENCES**

White H. A Heteroskedasticity-Consistent Covariance Matrix Estimator and a Direct Test for Heteroskedasticity. Econometrica. 1980;48(4):817-38.

Signature Page for VV-CLIN-004450 v1.0

Signature Page for VV-CLIN-004450 v1.0

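### The primary MMRM leaves out the randomisation stratum (baseline 24-hour UP), and the only recorded reason fits a covariate no longer used; the 90% CI is conservative if the stratum predicts change beyond log baseline UPCR

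*SAP*

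**What the plan says.** **Randomisation.** SAP Section 5.4: "The randomization will be stratified based on the baseline 24-hour UP", in two classes (1 to below 2 g/24 h, and 2 g/24 h or more). Patients are classed by the mean of two valid Week -2 collections, and the factor is held in both the IRS and the clinical database. Section 2.2 agrees.

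**Primary model.** In Section 7.1 the outcome is change in log 24-hour UPCR at Weeks 16 and 32. The terms are treatment, visit, "interaction term of treatment and scheduled visits, baseline 24-hour UPCR in log-scale (continuous), and patient as a random effect". The stratum is not among them.

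**Recorded reason.** Section 8 of SAP v1.0, appended to the current SAP, says "Use only the continuous baseline value of" 24-hour urine protein and removes the stratum because the two are correlated. The primary endpoint then was 24-hour UP. The Section 8 table of SAP Amendment 1 records the change of endpoint. Neither that table nor the current one returns to the stratum.

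**Where the stratum is used.** It appears in the stratified rank ANCOVA (Section 7.1.1), the CMH tests of the two responder endpoints (Table 2) and the subgroup analysis (Section 7.1.2).

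**Precision target.** Section 5.1 takes 9 placebo and 18 cemdisiran patients and states that these numbers "will provide a width of 0.80 (+/- 0.4) for the 90% confidence interval (CI) for treatment effect size estimate". Section 2.1 plans about 30 randomised, 20 and 10.

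**The concern.** The stratum was dropped because the model already carried the same quantity in continuous form. When the endpoint became UPCR, the covariate changed with it but the omission stayed. UP in g/24 h and UPCR differ by creatinine excretion, which depends on body size, sex and completeness of collection. Two patients with equal UPCR can therefore sit in different UP strata.

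Stratified randomisation balances the arms on the stratum. If the stratum carries prognostic information that log UPCR does not capture, leaving it out puts that variance in the residual. The model-based standard error then overstates the true variability of the treatment difference. The trial is sized only on CI width, so this gives away precision that the design has already secured.

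The rank ANCOVA does not fill the gap. It returns a p-value without an estimate or CI. It also differs from the MMRM in two ways, stratification and distributional assumption, so a disagreement between them could not be put down to non-normality alone. No planned analysis gives an overall stratum-adjusted estimate of the primary effect with its 90% CI.

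**Working it through.** **Step 1. Reproduce the plan's precision figure.** Inputs from Section 5.1: SD of the log ratio 0.597; 9 placebo and 18 cemdisiran patients; 90% two-sided CI.

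Width = 2 × 1.645 × 0.597 × √(1/9 + 1/18) = 2 × 1.645 × 0.597 × 0.4082 = 0.802, or ±0.401. This matches the stated 0.80. With the t quantile on 25 df the width is 0.833. With 10 and 20 patients and the normal quantile it is 0.761.

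**Step 2. Compare the model with and without the stratum.** Trials were simulated with 2:1 permuted blocks within two UP strata and analysed by Week 32 ANCOVA on log baseline UPCR, as a stand-in for the MMRM with complete data. The total within-arm SD was held at 0.597.

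Assumptions not in the SAP:
- correlation of log UP with log UPCR: 0.70 to 0.95
- stratum effect on log change beyond log UPCR: 0 to 0.6
- share of patients in the upper stratum: 50% (30% also tried)
- block size: 3 or 6

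Mean 90% CI width, N = 27, 50% in the upper stratum (8,000 trials per row; 4,000 where the effect is 0):

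| Extra stratum effect | Correlation | Without stratum | With stratum | Ratio | Coverage without |
|---|---|---|---|---|---|
| 0 | 0.70 | 0.825 | 0.833 | 0.991 | 89.2% |
| 0 | 0.85 | 0.822 | 0.831 | 0.988 | 90.6% |
| 0 | 0.95 | 0.824 | 0.837 | 0.985 | 90.1% |
| 0.2 | 0.70 | 0.838 | 0.836 | 1.002 | 90.4% |
| 0.2 | 0.85 | 0.832 | 0.836 | 0.995 | 89.9% |
| 0.2 | 0.95 | 0.834 | 0.841 | 0.991 | 90.2% |
| 0.4 | 0.70 | 0.839 | 0.814 | 1.031 | 91.3% |
| 0.4 | 0.85 | 0.834 | 0.817 | 1.020 | 90.3% |
| 0.4 | 0.95 | 0.832 | 0.824 | 1.009 | 90.2% |
| 0.6 | 0.70 | 0.837 | 0.764 | 1.096 | 92.2% |
| 0.6 | 0.85 | 0.826 | 0.774 | 1.067 | 91.3% |
| 0.6 | 0.95 | 0.817 | 0.779 | 1.049 | 91.1% |

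The Monte Carlo standard error of coverage is √(0.9 × 0.1/8,000) = 0.3 points (0.5 points at 4,000 trials). With the stratum in the model, coverage is about 90% throughout. Block size made no material difference, N = 30 gave the same pattern, and a 30% upper stratum gave ratios of 1.017 to 1.028 at 0.4 and 1.060 to 1.081 at 0.6.

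**Step 3. Check the table by hand.** If the stratum explains a share R² of the residual variance left after log UPCR, the ratio should be close to c/√(1 − R²), where c is the zero-effect ratio.
- Correlation 0.70, effect 0.4, R² = 0.077: 0.991/√0.923 = 1.03 (simulated 1.031).
- Correlation 0.70, effect 0.6, R² = 0.176: 0.991/√0.824 = 1.09 (simulated 1.096).

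The break-even R² is 1 − c²: 1 − 0.991² = 0.018 to 1 − 0.985² = 0.030. Adding the stratum pays once it explains roughly 2-3% of the residual variance. An effect of 0.2 explains 1.2-1.9%, so it roughly breaks even.

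**Step 4. A stratum that predicts change only through UPCR.** With log-UPCR slopes of -0.4 and -0.8, no extra stratum effect and correlation 0.85, the widths without and with the stratum are 0.786 vs 0.796 and 0.623 vs 0.630. The SAP model is about 1% narrower, with coverage of about 90%.

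**The case against.** **The loss is conditional.** A reader might infer that the CI is too wide whenever the stratum is prognostic. Step 4 shows otherwise: the stratum must predict change beyond log baseline UPCR. This objection stands and sets the terms of the point.

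**A visible loss needs a large effect.** Section 5.1 assumes that in the placebo arm "the geometric mean ratio of UPCR at Week 32 to baseline is 0.88 (log standard deviation [SD] 0.597" and that "the geometric mean ratio is 0.5, or a 50% reduction for the cemdisiran arm" applies to active treatment, so the assumed treatment effect is ln(0.5/0.88) = -0.565. A stratum effect of 0.6 beyond UPCR would be as large as that, and nothing in the SAP makes it likely. This also stands.

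**The planned precision is not shown to be missed.** A reader might infer that the omission pushes the CI past the planned ±0.4. With 0.597 taken as the SD of the log ratio itself, as Section 5.1 states it, the width without the stratum stays at about 0.82-0.84 for every assumed effect. The excess over 0.80 is already there when the effect is zero, and Step 1 shows that the t quantile alone gives 0.833. The point concerns precision that could be gained; no shortfall against the target is shown.

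**The recorded reason is correlation, and baseline UP and UPCR come from the same collections.** Correlation probably persists, so the omission lacks a current justification rather than being an error. But correlation with a continuous form of the stratifier itself is a stronger ground than correlation with a ratio that also varies with creatinine.

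**The stratum is handled elsewhere.** The rank ANCOVA gives a stratified test, the subgroup analysis gives effects within each stratum, and the CMH tests stratify because they have no continuous covariate. Different methods are not in themselves a contradiction. None of these yields an overall stratum-adjusted estimate with its CI.

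**Conclusion.** The point holds as a modest, inexpensive improvement. The stratum is missing from the primary model, the remaining covariate is a different variable from the stratifier, and no reason applying to UPCR is recorded.

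Over the assumed range, the effect on CI width runs from a gain of about 1% to a loss of about 10%. Since width varies with 1/√N, the 5-10% at an effect of 0.6 is worth 1.049² - 1 = 10% to 1.096² - 1 = 20% more patients; the 1-3% at 0.4 is worth about 2-6%. The size cannot be fixed from the SAP, and missing Week 32 data were not simulated.

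A reader might infer bias or an inflated false-positive rate. Neither follows: the arms are balanced on the stratum by design, the estimate is unbiased with or without it, and any error in the CI is on the conservative side. All comparisons are descriptive (Section 5.5), so no decision rule changes.

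A reader might also extend the point to every MMRM. It does not reach the 24-hour UP model if that model's covariate is log baseline 24-hour UP, because the recorded reason still applies there.

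**What to change.** In Section 7.1, add the randomisation stratum (baseline 24-hour UP, 1 to below 2 versus 2 g/24 h or more) as a fixed effect beside log baseline 24-hour UPCR. Specify the value as randomised in the IRS, since Section 5.4 holds the factor in two places. Make the same change in the spot UPCR MMRM in Table 2. Report the resulting stratum-adjusted estimate and 90% CI, and record the change in Section 8. State that the 24-hour UP MMRM uses log baseline 24-hour UP as its covariate; the stratum term is then not needed there.

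If the sponsor prefers the present model, give a reason that applies to UPCR and add the stratum-adjusted MMRM as a sensitivity analysis with its estimate and 90% CI. That route is also the safer one if Week 32 results by arm are already known to those amending the SAP, since Section 2.3 leaves sponsor personnel unblinded.

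The cost is one model term and one degree of freedom, about 1% of CI width if the stratum turns out to add nothing.

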8. CHANGES TO PLANNED ANALYSES

Change from SAP V1.0	Detailed Description/Rationale
Change the primary and secondary endpoints	Per protocol amendment 3
The working correlation structure in the MMRM model for the analysis of the primary endpoint is changed to unstructured	Since there are only two post baseline assessments, the unstructured working correlation will provide robust estimates by REML.
Section 7.8 and Appendix 10 are added	To address COVID-19 pandemic impact
Various editorial changes	To improve clarity

9. **REFERENCES**

White H. A Heteroskedasticity-Consistent Covariance Matrix Estimator and a Direct Test for Heteroskedasticity. Econometrica. 1980;48(4):817-38.

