The resulting 24-hour UP at each visit will be log transformed for analyses [Fellstrom 2017; Li 2006]. The primary analysis will be performed using a restricted maximum likelihood (REML) based Mixed-Effect Model Repeated Measures (MMRM) approach. The outcome variable is change from baseline in 24-hour urine protein in log-scale at week 16 and week 32 visits. Analysis will include fixed effects of treatment (cemdisiran vs. placebo), scheduled visits (week 16 and week 32), interaction term of treatment and scheduled visits, baseline 24-hour urine protein in log-scale (continuous), and patient as a random effect. Robust errors [White 1980] will be used to model the within-patient errors. If the fit of covariance structure with the robust errors fails to converge, a compound symmetric correlation structure will be used. At each visit, least square (LS) means ($\hat{\mu}_j$) with corresponding standard errors (SEM) and 90% CI will be displayed by treatment arm. The primary comparison is the LS mean treatment difference (cemdisiran – placebo) in percent change of 24-hour urine protein at week 32 visit from baseline. This LS mean difference will be presented along with corresponding standard errors (SEMs), 90% CIs and p-value from the model.

The following results will also be presented:

Placebo-adjusted geometric mean percent change at week 32 visit:

$$\frac{GM\left(\frac{UP \text{ at week32}}{UP \text{ at baseline}}\right)_{cemdisiran} - GM\left(\frac{UP \text{ at week32}}{UP \text{ at baseline}}\right)_{placebo}}{GM\left(\frac{UP \text{ at week32}}{UP \text{ at baseline}}\right)_{placebo}} * 100$$

= $[\exp(\delta) - 1] * 100$ where δ is the LS mean treatment difference between the two arms from the MMRM model above.

• The 90% CI for the placebo-adjusted geometric mean percent change:

[(exp(lower bound for δ) - 1) * 100, (exp(upper bound for δ) - 1) * 100]

In addition, the geometric mean for the ratio from baseline at week 32 visit in 24-hour UP and 90% confidence intervals for each treatment group will be presented using respective LS means $(\hat{\mu}_i)$ and corresponding 90% confidence intervals (j=0 if placebo and j=1 if cemdisiran):

 $exp(\hat{\mu}_j)$ and $\left[exp(lower bound for \mu_j), exp(upper bound for \mu_j)\right]$

Descriptive statistics will also be generated by treatment arm at each scheduled visit. Geometric Mean (+/- SEM) figures of the ratio to baseline by treatment arm will be plotted as well as individual spaghetti plots.

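### The primary MMRM carries a redundant random patient effect, and its independence fallback does not say whether that effect stays

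*SAP*

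**What the plan says.** The current SAP, Section 7.1, defines the response as follows: "The outcome variable is change from baseline in 24-hour UPCR in log-scale at week 16 and week 32 visits". The model terms include treatment, visit, "interaction term of treatment and scheduled visits, baseline 24-hour UPCR in log-scale (continuous), and patient as a random effect". The next sentence reads: "Unstructured working correlation will be used to model the within-patient errors". The fallback follows directly: "If the fit of covariance structure fails to converge, independent correlation structure will be used". The section does not define a failure to converge, does not say whether the patient effect survives the switch, and names no intermediate structure.

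Two change logs bound with the SAP give the reasoning. Section 8 of the first amendment supports the unstructured choice: "Since there are only two post baseline assessments, the unstructured working correlation will provide robust estimates by REML". Section 8 of version 1.0 explains why MMRM replaced a Week 32 linear model: "To allow use of all the data when" modelling the primary endpoint, including data from patients without a Week 32 value. As history only, Section 7.1 of version 1.0 said that if the fit "fails to converge, a compound symmetric correlation structure will be used". The logs explain the move to unstructured but not the move to an independent fallback.

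Section 7.2 (Table 2) uses a similar MMRM for 24-hour proteinuria, and the second sensitivity analysis in Section 7.1.1 reuses the same MMRM.

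**The concern.** With two post-baseline visits, an unstructured error matrix already describes the within-patient covariance completely, so a random intercept has nothing left to estimate. The specification thus builds in a singularity, and the next sentence makes the choice of primary model depend on whether the fit is declared to have failed. That choice fixes the model behind the Week 32 estimate, its 90% CI and its p-value.

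The fallback matters because MMRM was adopted so that patients without Week 32 data could contribute. They do so only through the modelled correlation between Week 16 and Week 32. The mITT definition in Section 4.1 admits patients with a single post-baseline value, and Section 5.6 does not impute. Whether the fallback keeps that correlation is therefore a real question, and the SAP leaves it open.

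**Working it through.** **Plan's own figure.** Section 5.1 gives a log SD of 0.597, with 9 placebo and 18 cemdisiran patients.
- SE = 0.597 × √(1/9 + 1/18) = 0.2437.
- 90% half-width = 1.645 × 0.2437 = 0.401; width = 0.802.

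The stated 0.80 reproduces and does not depend on this point. The planned effect is ln(0.5/0.88) = -0.565.

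**Parameter count.** Let σ_b² be the patient variance and r11, r12, r22 the residual elements. The marginal covariance is
- v11 = σ_b² + r11
- v12 = σ_b² + r12
- v22 = σ_b² + r22

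Four parameters map to three elements, and the map has rank 3. Adding c to σ_b² and subtracting c from every residual element leaves the marginal covariance, and so the likelihood, unchanged. In one simulated dataset the fitted marginal matrix was [0.303, 0.174; 0.174, 0.260]. Setting σ_b² to 0, 0.05, 0.10 and 0.15 gave the same REML criterion (-7.2451) and the same Week 32 difference (-0.6815) each time. The variance components are not identifiable; the treatment contrast is.

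**Fallback, patient effect kept.** The marginal covariance has σ_b² + σ² on the diagonal and σ_b² off it. That is compound symmetry with 2 parameters, and the correlation is retained. It forces equal variances, although Section 7.1 uses one collection at Week 16 and the mean of two at Week 32. The cost depends on how unequal the SDs are, which the SAP does not give:
- Assumed SDs 0.634 and 0.597 (ratio 1.06): the Week 32 difference averaged within 0.004 log units of unstructured in simulation.
- Assumed SDs 0.75 and 0.597, correlation 0.5, complete data: the 90% CI width is 0.905 against 0.798 for unstructured, with coverage 97% against 92%.

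**Fallback, patient effect dropped.** Week 16 and Week 32 are treated as uncorrelated. A patient with only Week 16 data then reaches the Week 32 contrast only through the shared baseline slope and residual variance.

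*Closed-form illustration.* Assumptions: SDs 0.634 (Week 16) and 0.597 (Week 32), Week 16 effect 70% of the Week 32 effect, and patients above baseline at Week 16 lost with probability 0.5 to 0.8. At correlation 0.7, missingness is 10–16% on cemdisiran and 21–34% on placebo.
- Correlation 0.7: bias +0.037 to +0.083, or 7–15% of 0.565.
- Correlation 0.5: bias +0.027 to +0.060, or 5–11%.

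*Simulation.* 300 trials of 20 and 10 patients, SD 0.597 at both visits, correlation 0.5:

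| Week 32 missingness | Model | Bias | 90% CI coverage |
|---|---|---|---|
| Placebo 30%, driven by Week 16; cemdisiran 10%, random | Unstructured | 0.012 | 88% |
| | Compound symmetry | 0.009 | 91% |
| | Independence | 0.138 | 83% |
| Same Week 16 rule in both arms (26–27%) | Unstructured | -0.002 | 91% |
| | Independence | 0.002 | 91% |

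Monte Carlo error is about 0.016 on bias and 1.7 points on coverage. With complete data or 10% random loss, independence performs like unstructured (coverage 90–93% against 91–93%).

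**The case against.** The strongest reply is that little goes wrong in practice. Unidentifiable variance components are not the same as non-convergence. In simulated fits of the four-parameter model (200 trials per scenario), a generic quasi-Newton optimiser met its criterion in 99–100% of datasets, and the Week 32 estimate matched unstructured alone to four decimals. This stands: failure is possible and software differs, but nothing shows that it is likely.

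A reader might also infer that the fallback defeats the purpose of MMRM outright. The text does not support that. The fallback sentence follows the one on within-patient errors, and nothing removes the patient effect. Read literally, the fallback is compound symmetry, and the quoted biases do not apply to it.

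One may add that the random-effect phrase could merely name the patient as the clustering unit. That reading rescues the planned model, but it then makes the independent fallback a true independence model. Either way one of the two sentences needs repair.

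Mitigation in the plan also counts. Patients are encouraged to complete visits, and data after treatment discontinuation are used (Section 5.6). The rank ANCOVA does not use the MMRM covariance, and spot-urine imputation is available (Section 7.1.1). All comparisons are descriptive (Section 5.5). These lower the severity. They do not settle the wording: the rank ANCOVA uses Week 32 change only, and the imputation analysis reuses the same MMRM and may be omitted.

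**Conclusion.** The over-parameterisation is certain: 4 variance parameters for 3 identifiable elements. It leaves an accepted estimate, its standard error and the planned CI width unchanged. What it adds is an avoidable route into a fallback that the SAP does not define fully.

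The size of the harm is conditional. It needs a declared failure, removal of the patient effect, and loss that differs between arms and depends on Week 16 values. Under the assumed inputs above, the bias is then +0.03 to +0.08 log units towards no effect, or 0.11 to 0.34 of the planned SE of 0.2437. A harsher assumed pattern, with dependent loss on placebo only, gives +0.138 (24% of 0.565). With the same rule in both arms it is near zero. The SAP gives no correlation, Week 16 SD or missingness rate, so these figures are illustrations and not forecasts. Severity is moderate.

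**What to change.** In Section 7.1, end the list of model terms at the continuous baseline covariate, so that the last clause of "baseline 24-hour UPCR in log-scale (continuous), and patient as a random effect" is deleted. Keep REML with an unstructured 2×2 residual covariance. Replace the fallback sentence with wording such as: *If the unstructured model does not converge, a compound symmetric residual covariance will be used, without a patient random effect.* Add one line on what counts as a failure.

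Heterogeneous compound symmetry should not be listed as the fallback. For two visits it has two variances and one correlation, which is the unstructured model again and would refit what had just failed.

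Apply the same text to the 24-hour proteinuria MMRM in Section 7.2 (Table 2); the second sensitivity analysis in Section 7.1.1 inherits it. The cost is two or three sentences of SAP text and one line of code. Any accepted fit of the present model is unchanged.
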